8.1 Inclusion Criteria

Subjects will be eligible if they meet all of the following criteria:

1. Willing and able to provide informed consent for the trial, written, electronic, verbal, or other method deemed acceptable by the institution and IRB.
2. Subjects between ≥ 18 and ≤ 65 years of age.
3. Subjects found positive for SARS-CoV-2 either by rapid antigen test or by reverse transcription polymerase chain reaction (RT-PCR) using ICMR-validated kit.

Note: Test need not be repeated in those with possession of confirmed positive report but positive result test date must be ≤ 5 days of first dose of study drug.

4. Mild or Moderate COVID-19 as per latest updated version of CLINICAL MANAGEMENT PROTOCOL for COVID-19 (in Adults) released by Government of India Ministry of Health and Family Welfare Directorate General of Health Services (EMR Division).
5. The effects of brequinar on the developing human fetus are unknown. For this reason, women of child-bearing potential and men must agree to use adequate contraception (hormonal or barrier method of birth control; abstinence) prior to study entry and for the duration of study participation. Should a woman become pregnant or suspect she is pregnant while she or her partner is participating in this study, she should inform her treating physician immediately. Men and women treated or enrolled on this protocol must also agree to use adequate contraception for the duration of study participation, and for 90 days after completion of brequinar administration.
6. Male subjects must agree to refrain from sperm donation and female subjects must agree to refrain from ovum donation from initial study drug administration until 90 days after the last dose of brequinar.
7. At least one non-respiratory COVID-19 symptom characterized as moderate to severe by the Investigator including but not limited to fatigue, chills, fever, body aches, nasal congestion, nausea, vomiting, or other sign or symptom commonly associated with COVID-19 in the opinion of the investigator. Symptom onset must be ≤ 5 days prior to first dose. Subject must have one or more signs/symptoms present at first dose.
8. Willing to participate in the PK subset if at one of the identified sites.
9. Able to swallow capsules.

Protocol for clinical study of Brequinar
 Protocol No.: 21-VIN-0372
 Version No.: 2.1; Dated: 29 Dec 2021
 Supersedes: 02; Date of Supersedes: 30 Sep 2021

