8.2 Exclusion Criteria

Subjects will not be eligible for this study if any of the following in present at the time of study inclusion:

1. Have an oxygen saturation of <90% while breathing ambient air.
2. Any physical examination findings and/or history of any illness that, in the opinion of the study investigator, might confound the results of the study or pose an additional risk to the subject.
3. Nursing women or women of childbearing potential (WOCBP) with a positive pregnancy test.
4. Treatment with another DHODH inhibitor (e.g., leflunomide, teriflunomide) or other agents known to cause bone marrow suppression leading to thrombocytopenia.
5. Ongoing treatment with aspirin and or dipyridamole, famotidine or cimetidine. Remdesivir and ivermectin are prohibited through Study Day 8. Steroids are permitted per the guidelines.
6. Platelets \leq 125,000 cell/mm³.
7. Hemoglobin <10 gm/dL.
8. Absolute neutrophil count <1000 cells/mm³.
9. Renal dysfunction, i.e., creatinine clearance <30 mL/min.
10. AST or ALT $>$ 3 x ULN, or total bilirubin $>$ ULN. Gilbert's Syndrome is allowed.
11. Bleeding disorders or blood loss requiring transfusion in the six weeks preceding enrollment.
12. Ongoing gastrointestinal ulcer, or gastrointestinal bleeding within 6 weeks of first dose.
13. HIV, Chronic hepatitis B infection, active hepatitis C infection, active liver disease and/or cirrhosis per subject report.
14. Heart failure, current uncontrolled cardiovascular disease, including unstable angina, uncontrolled arrhythmias, major adverse cardiac event within 6 months (e.g., stroke, myocardial infarction, hospitalization due to heart failure, or revascularization procedure).

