8.3 Withdrawal Criteria

Subjects may voluntarily withdraw from the study at any time without assigning any reason thereof by withdrawing their consent. They may be considered withdrawn if they state an intention to withdraw, or fail to return for visits, or become lost to follow up for any other reason.

If premature withdrawal occurs for any reason, the investigator must determine the primary reason for a patient's premature withdrawal from the study and record this information in the CRF. For patients who are lost to follow-up (i.e., those patients whose status is unclear because they fail to appear for study visits without stating an intention to withdraw), the investigator should show "due diligence" by documenting in the source documents steps taken to contact the patient, e.g., dates of telephone calls, other means of communication even though patient is unwilling to attend further visits etc.

If study participation is discontinued, the final evaluation will be performed as completely as possible. Any comments (spontaneous or elicited) or complaints made by the patient and the reason for termination, date of stopping the study medication and the total amount of study medication must be recorded in the source documents or CRFs.

Protocol for clinical study of Brequinar

Protocol No.: 21-VIN-0372

Version No.: 2.1; Dated: 29 Dec 2021

Supersedes: 02; Date of Supersedes: 30 Sep 2021

Criteria for a withdrawal of patients from clinical study:

The subject may be withdrawn from the trial at the discretion of the investigator or the sponsor, if judged non-compliant with trial procedures or due to safety concern.

A subject must in addition be withdrawn from treatment with IMP if the following applies:

- AE requiring permanent discontinuation of study drug.
- The subject suffers from significant intercurrent illness or undergoes surgery requiring study discontinuation during the course of the study.
- Any subject who requires the use of an unacceptable concomitant medicine.
- If the Investigator believes it is not in the subject's best interest to continue.
- The subject wishes to withdraw his/her consent.
- Any other justifiable reason, which should be adequately documented.
- Any subject whose condition worsens, requiring treatment with immunomodulators including but not limited to tocilizumab and / or antiviral drugs including but not limited to remdesivir as per the best judgement of the Investigator.

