10.2.5 Concomitant medication

Any allowable concomitant medication being taken by the subject should be continued on same dose during the study. Any change in the dose needs to be documented and subjects can continue in the study if the investigator deems proper. Administration of the following medications is not permitted after screening until after the end of each subject's study participation.

Prohibited Medications:

The following concomitant medications, products or procedures will not be allowed while enrolled in the study:

- Hydroxychloroquine
- Ivermectin
- Immunomodulators such as tocilizumab
- Antiviral drugs or drugs with antiviral potential including but not limited to remdesivir

The use of any of the above mentioned medications/procedure will result in withdrawal of the subject from the study.

Note: This list of drug is not exhaustive. However, any drug which is not mentioned above and having a possible on study drug efficacy and safety, should be confirmed with Medical Monitor/Medical Expert.

Protocol for clinical study of Brequinar

Protocol No.: 21-VIN-0372

Version No.: 2.1; Dated: 29 Dec 2021

Supersedes: 02; Date of Supersedes: 30 Sep 2021

Permissible Medications: Other than those prohibited.

Standard treatment [(Standard Of Care (SOC)] provided in all the arms will be per the latest updated version of CLINICAL MANAGEMENT PROTOCOL for COVID-19 (in adults) released by Government of India Ministry of Health and Family Welfare Directorate General of Health Services (EMR Division).

If drug therapy other than that specified in the protocol is required prior to or during the study period, decisions shall be taken by the investigator to continue or discontinue the subject based on the following:

- The pharmacology and pharmacokinetic of the non-study medication.
- The likelihood of a drug–drug interaction.
- The time and duration of administration of the non-study medicine.

The start and stop date of concomitant medication use during the study should be recorded in source data. All such instances will be recorded and reported in the final report with details of start date, stop date and reason for medication use.

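### Aspirin is barred at study entry but named in no on-study restriction, so nothing in the protocol body tells a subject in advance to avoid over-the-counter aspirin

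*Combined protocol and SAP*

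**What the plan says.** All references are to protocol version 2.1.

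- **At entry.** The exclusion list in section 8.2 opens with "Subjects will not be eligible for this study if any of the following in present at the time of study inclusion". Criterion 5 then bars "Ongoing treatment with aspirin and or dipyridamole, famotidine or cimetidine". The next sentence of the same criterion sets an on-study period for two other drugs: "Remdesivir and ivermectin are prohibited through Study Day 8".
- **On study.** Section 10.2.5 prohibits hydroxychloroquine, ivermectin, immunomodulators such as tocilizumab, and antivirals. Using any of them means withdrawal from the study. It then says "Permissible Medications: Other than those prohibited". The short list in section 9.11 covers antivirals only.
- **Backstops.** Section 10.2.5 also says "This list of drug is not exhaustive" and sends unlisted drugs that may bear on efficacy or safety to the Medical Monitor. It asks the investigator to weigh drug interactions. Section 8.3 stops study drug for "Any subject who requires the use of an unacceptable concomitant medicine", a term it does not define.
- **Setting.** Inclusion 7 asks for at least one non-respiratory symptom, "including but not limited to fatigue, chills, fever, body aches, nasal congestion, nausea, vomiting" or another. Section 9.2 provides for home-quarantined subjects and remote visits, with subjects recording their own medicines on a diary card.

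**The concern.** An entry bar on aspirin has no named counterpart once dosing starts, and aspirin needs no prescriber. A subject at home with fever or aches could take it during the five dosing days before anyone at the site is asked.

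What is at stake is mainly subject safety. Section 5.5 says the combination has not been given clinically before and that its bleeding risk compared with either drug alone is not known. The same section lists thrombocytopenia among the commonest side effects of brequinar in cancer patients at higher doses. Section 5.3 describes dipyridamole as an inhibitor of platelet function. Aspirin with dipyridamole is an established pairing (section 5.6). Aspirin on top of both study drugs would be new.

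A secondary issue is attribution. Under section 12.13, an event with reasonable timing that another drug could also explain is rated Possible, which counts as Related. Under section 12.9, one related Grade 3 event prevents a cohort from being declared safe.

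**Working it through.** **Text comparison.** The plan states no figure on this point, so the first check is of wording.

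| Place | Aspirin named? | When it applies |
|---|---|---|
| 8.2, exclusion 5 | Yes, ongoing treatment | At inclusion |
| 8.2, exclusion 5, second sentence | No (remdesivir, ivermectin) | Through Day 8 |
| 9.11 prohibited medications | No (antivirals) | On study |
| 10.2.5 prohibited list | No | On study |
| 10.2.5 open-list note, Medical Monitor, interaction review | Not by name; could be caught | When someone asks |
| 8.3 withdrawal from study drug | Not by name; could be caught | Once a drug is judged unacceptable |
| 5.5 bleeding-symptom reporting | Not applicable | After symptoms appear |
| 9.11 and 28.0 platelet counts | Not applicable | After Day 1: Days 8, 15 and 29 |

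No on-study row names aspirin. The rows that could catch it depend on a query or a judgement, and the monitoring rows act after exposure.

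**Who is exposed, and for how long (from the documents).**

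- Combination-treated subjects: 4 cohorts × 8 + about 32 in the expansion = 64.
- Study drug runs on Days 1 to 5 and the cohort decision uses Day 15 results, so 15 − 5 = 10 days of that window follow the last dose.
- Concomitant medicines are asked about on Days 1 to 8, 12 and 15: 8 + 2 = 10 contact days. These contacts detect use; they do not by themselves prevent it.

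**Illustration (assumed rates).** The documents give no rate of aspirin use, so let *p* be the share of subjects who take it, from 2% to 10%.

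- Expected users among 64 = 64*p*: 1.28 at 2%, 3.2 at 5%, 6.4 at 10%.
- Chance of at least one user among the 8 combination subjects in a cohort = 1 − (1 − *p*)^8: 14.9% at 2%, 33.7% at 5%, 57.0% at 10%.

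Let *q* be an assumed added risk, per user, of a Grade 3 or higher event rated Related. A cohort has 8 + 4 = 12 brequinar-treated subjects. The chance that it fails for this reason alone is 1 − (1 − *pq*)^12:

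- *p* = 2%, *q* = 1%: 0.24%
- *p* = 5%, *q* = 2%: 1.19%
- *p* = 10%, *q* = 5%: 5.84%

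Some exposure is therefore plausible across the assumed range, but the effect on escalation is small.

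**The case against.** The strongest reply is that the existing checks already cover this. Read as a whole, section 10.2.5 does not authorise aspirin: the permissive line follows a note that the list is open and that drugs bearing on safety need confirmation. Section 8.2 also excludes low platelets, bleeding disorders and recent gastrointestinal bleeding. Section 5.5 tells subjects to report bleeding and promises close attention to laboratory reports. All of that stands and narrows the gap. It does not close it, because none of it reaches the subject before a first over-the-counter dose.

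A second reply also stands. The consent form, the diary card and the national guideline that governs standard of care are not in the documents. Any of them may already steer subjects away from aspirin. The point is limited to the protocol body.

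A reader might infer more than the text supports:

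- *That subjects typically have fever and are at home.* Inclusion 7 is an open list and does not require fever or aches. Section 9.3 allows a hospital stay covering all dosing days at the investigator's discretion. No proportion at home is given.
- *That the sponsor barred aspirin because of bleeding, so the reason must persist.* Exclusion 5 gives no reason and groups aspirin with famotidine and cimetidine. It also bars ongoing treatment, which is not the same as an occasional dose.
- *That the same point should be pressed for every drug in exclusions 4 and 5.* The wording gap is shared, but a new start of non-study dipyridamole or a marrow suppressant is improbable here, and the documents state no bleeding concern for famotidine or cimetidine.
- *That any aspirin use should end study treatment.* In a five-day course with arms of 8 or 4, an automatic stop could lose more than it protects.

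**Conclusion.** The point holds in a limited form and is worth considering. Aspirin is barred at inclusion and appears in no on-study list, and the protocol body contains no advance instruction to subjects. The combination's relative bleeding risk is unknown, and prevention is cheap, so the gap should be closed on safety grounds.

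The size is modest. About 64 subjects would be on the combination. The 1.3 to 6.4 exposed rest entirely on the assumed 2% to 10% usage.

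A reader might infer that aspirin-related bleeding would distort dose escalation. The documents do not support that. An event with improbable timing can be rated Unlikely and count as Not Related, so misattribution is not automatic. Where it did occur, it would hold escalation back, which is the cautious direction. Even with assumed inputs, cohort failure for this reason alone is 0.2% to 5.8%.

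**What to change.** 1. In section 10.2.5, name aspirin as restricted from Day 1 to Day 15. Use a list separate from the prohibited list, because use of a prohibited drug triggers study withdrawal. Day 15 is proposed to match the cohort safety decision.
2. Reword the permissive line to *Other than those prohibited or restricted in this section*.
3. Add one diary-card line telling subjects not to self-medicate with aspirin and naming a permitted alternative for fever and aches. The sponsor's medical team should choose it.
4. If aspirin is taken, stop it where medically possible and notify the Medical Monitor, who decides whether study drug continues. Keep the subject in follow-up.
5. Flag the use from the concomitant-medication data already collected, and give the flag to the unblinded CRO physician for the cohort review.

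The cost is a short wording change, one diary-card line and one flag from existing data, with no new visit, sample or assay. A few subjects may need a different antipyretic. If the consent form, diary card or guideline already gives this advice, only the 10.2.5 wording and the flag remain to be done.

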11.0 EFFICACY ASSESSMENT

Efficacy will primarily be assessed by reduction in SARS-CoV-2 RNA levels as measured by the quantitative RTPCR test for SARS COV2 in brequinar-dipyridamole treated subjects compared to brequinar-only and placebo-treated subjects through Day 29.

Symptom improvement will be defined in the SAP. Clinical improvement for the ordinal scale will be defined as defined as a 2-point or greater improvement on an 8-point WHO ordinal scale in every subject measured on each designated day (i.e Screening, Days 1, 4, 8, 12, 15, 22, 29), until Day 29 from the date of randomization. This scale has been used in the current COVID-19 outbreak.

Ordinal Scale for Clinical Improvement

Patient State	Descriptor	Score
Uninfected	No clinical or virological evidence of infection	0
Ambulatory	No limitaion of activities	1
	Limitation of activities	2
Hospitalized Mild disease	Hospitalized, no oxygen therapy	3
	Oxygen by mask or nasal prongs	4

Protocol for clinical study of Brequinar

Protocol No.: 21-VIN-0372

Version No.: 2.1; Dated: 29 Dec 2021

Supersedes: 02; Date of Supersedes: 30 Sep 2021

Hospitalized Severe Disease	Non-invasive ventilation or high-flow oxygen	5
	Intubation and mechanical ventilation	6
	Ventilation + additional organ support – pressors, RRT, ECMO	7
Dead	Death	8

12.0 SAFETY ASSESSMENT

The study will include the following evaluations of safety and tolerability according to the time points provided in the [3.2 Schedule of Activities](#).

12.1 Demographic Characteristics

Demographic data (subject reported / measured height and weight, age, sex and race/ethnicity) will be captured as specified in the [3.2 Schedule of Activities](#).

12.2 Medical and Medication History

The Investigator or his/her designee will obtain a detailed medical history and medication history as specified in the [3.2 Schedule of Activities](#).

Medical history includes clinically significant diseases within 30 days or ongoing and history of current illness (date of symptom onset or change in baseline co-morbidity thought to be due to COVID-19 infection).

Information on all medications (e.g., prescription drugs, over-the-counter drugs, herbal or homeopathic remedies, nutritional supplements) used by the participant within 30 days prior to baseline visit will be recorded on the CRF.

Concomitant medications administered from screening to randomization will be recorded as a medication history on the CRF.

12.3 Physical Examination

This evaluation will include an examination of general appearance, skin, neck (including thyroid), eyes, ears, nose, throat, lungs, heart, abdomen, back, lymph nodes, extremities and basic nervous system evaluation. Information about the physical examination must be present in the source documentation at the study site. If any abnormalities are noted during the study, the participant may be referred to another doctor. The investigator should use his or her clinical judgment for appropriate treatment and/or medical referral.

Clinically significant findings/abnormalities prior to the signing of ICF must be included in the relevant medical history/current medical conditions section of the CRF. Significant findings after the start of the IMPs that meet the definition of an AE must be recorded in the Adverse Event section of the CRF. Physical examination should

Protocol for clinical study of Brequinar

Protocol No.: 21-VIN-0372

Version No.: 2.1; Dated: 29 Dec 2021

Supersedes: 02; Date of Supersedes: 30 Sep 2021

be done at specified in the [3.2 Schedule of Activities](#). Changes from baseline abnormalities should be recorded in participant notes. New or worsened clinically significant abnormalities should be recorded as adverse events on the Adverse Event CRF.

12.4 Vital Signs

Vital signs will include measurements of body temperature, respiratory rate, heart rate and SpO₂ taken with the participant in a seated position after resting for 5 minutes. Vital signs will be measured at specified in the [3.2 Schedule of Activities](#). If the subject needs to be assessed remotely due to COVID-19 restrictions or for other reasons, the subject is to be provided with a pulse oximeter and digital thermometer.

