5.3 Safety of Dipyridamole

Introduction:

Dipyridamole was first approved for use in 1961 as an adjunct to coumarin anticoagulants in the prevention of postoperative thromboembolic complications of cardiac valve replacement. The primary therapeutic actions of dipyridamole relate to its activity in (1) inhibiting platelet function and aggregation and (2) vasodilatation.

Dipyridamole inhibits the uptake of adenosine into platelets, endothelial cells and erythrocytes in vitro and in vivo; the inhibition occurs in a dose-dependent manner at therapeutic concentrations (0.5–1.9 µg/mL). This inhibition results in an increase in local concentrations of adenosine which acts on the platelet A₂-receptor thereby stimulating platelet adenylate cyclase and increasing platelet cyclic-3',5'-adenosine monophosphate (cAMP) levels. Via this mechanism, platelet aggregation is inhibited in response to various stimuli such as platelet activating factor (PAF), collagen and adenosine diphosphate (ADP).

Dipyridamole also inhibits phosphodiesterase (PDE) in various tissues. While the inhibition of cAMP-PDE is weak, therapeutic levels of dipyridamole inhibit cyclic-3',5'-guanosine monophosphate-PDE (cGMP-PDE), thereby augmenting the increase in cGMP produced by EDRF (endothelium-derived relaxing factor, now identified as nitric oxide).

Preclinical study data:

In addition to the effects upon platelet function, dipyridamole can cause vasodilatation.

Hemodynamics:

In dogs intraduodenal doses of dipyridamole of 0.5 to 4.0 mg/kg produced dose-related decreases in systemic and coronary vascular resistance leading to decreases in systemic blood pressure and increases in coronary blood flow. Onset of action was in about 24 minutes and effects persisted for about 3 hours.

Similar effects were observed following intravenous dipyridamole in doses ranging from 0.025 to 2.0 mg/kg.

In man the same qualitative hemodynamic effects have been observed. However, acute intravenous administration of dipyridamole may worsen regional myocardial perfusion distal to partial occlusion of coronary arteries.

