Dipyridamole will be used in this study as a pyrimidine salvage inhibitor when co-administered with brequinar (see Rationale below). When used per the labeled indications of stroke prevention and inhibitor of blood clot formation, adverse reactions at therapeutic doses are usually minimal and transient. In combination with warfarin, the dipyridamole label reports dizziness (13.6%), abdominal distress (6.1%), headache (2.3%), and rash (2.3%). Reactions from uncontrolled studies include diarrhea, flushing, and pruritus. Angina pectoris has been reported rarely and there have been rare reports of liver dysfunction. In post-marketing reporting experience, there have been rare reports of hypersensitivity reactions (such as rash, urticaria, severe bronchospasm, and angioedema), larynx edema, fatigue, malaise, myalgia, arthritis, nausea, dyspepsia, paresthesia, hepatitis, thrombocytopenia, alopecia, cholelithiasis, hypotension, palpitation, and tachycardia. In the case of real or suspected overdose, symptoms may occur such as warm feeling, flushes, sweating, restlessness, and feeling of weakness and dizziness. There is an increased risk of thrombocytopenia when taking dipyridamole. There are no clinical data to suggest that dipyridamole is beneficial for treating COVID-19.

Co-Administration of Brequinar and Dipyridamole:

This combination has not previously been tested in the clinic. There is a potential for increased bleeding when taking either drug as well as the combination, and the risk compared to brequinar or dipyridamole when administered alone is unknown. To address any potential increased risk, careful attention will be paid to laboratory reports and any increased signs or symptoms of bleeding during this study.

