9.11 Clinical Safety Measures

It is the responsibility of the investigator to ensure that adequate medical supervision and care is available for the study subjects during the study to ensure their utmost safety and well being.

- Demography (subject reported / measured height and weight, age, sex and race/ethnicity): At screening
- Medical history (relevant within 30 days or ongoing) / History of current illness (date of symptom onset or change in baseline co-morbidity thought to be due to COVID-19 infection): At screening
- Physical Examination (subject self-reported / examiner evaluated): At screening
- Vital signs (body temperature, respiratory rate, heart rate, SpO₂) assessment: At screening, Day 4 (± 8 hrs), Day 8 (± 8 hrs), Day 12 (± 1 day), Day 15 (± 1 day), Day 22 (± 1 day), End of study [EoS; Day 29 (± 2 day)].

Note: If subject is hospitalized, Vital signs assessment will be done on daily basis by site team during hospitalization through Day 8 then following the Vital signs visits as listed above.

- Hematology, biochemistry and urine analysis: At screening, Day 1 unless same day as Screening visit, Day 8 (± 8 hrs), Day 15 (± 1 day), End of study [EoS; Day 29 (± 2 day)].

- HCV, HbSAg, HIV Test: At screening

- Serum pregnancy test (Women of child bearing potential (WOCBP)): At screening.

- Urine pregnancy test (WOCBP): End of study [EoS; Day 29 (± 2 day)].

Note: WOCBP: A premenopausal female capable of becoming pregnant

- Rapid antigen test / SARS-CoV-2 RT-PCR Qualitative (in a clinically relevant specimen (Naso-Oro-

Protocol for clinical study of Brequinar

Protocol No.: 21-VIN-0372

Version No.: 2.1; Dated: 29 Dec 2021

Supersedes: 02; Date of Supersedes: 30 Sep 2021

Pharyngeal as appropriate)): Screening

Note: Test need not be repeated in those with possession of confirmed positive report. Date of positive report must be \leq 5 days prior to randomization.

- RT-PCR Quantitative Viral (in a clinically relevant specimen (Naso-Oro-Pharyngeal as appropriate)): Day 1 (Prior to dosing), Day 4 (\pm 8 hrs), Day 8 (\pm 8 hrs), Day 12 (\pm 1 day), Day 15 (\pm 1 day), Day 22 (\pm 1 day) and End of study [EoS; Day 29 (\pm 2 day)]
- Ordinal Scale Assessment: Screening, Day 8 (\pm 8 hrs), Day 15 (\pm 1 day), Day 22 (\pm 1 day) and End of study [EoS; Day 29 (\pm 2 day)]

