12.5 Abnormal Vital Sign Values

Not every vital sign abnormality qualifies as an adverse event. A vital sign result must be reported as an adverse event if it meets any of the following criteria:

- Is accompanied by clinical symptoms
- Results in a change in study treatment (e.g., dosage modification, treatment interruption, or treatment discontinuation)
- Results in a medical intervention (e.g., potassium supplementation for hypokalemia)
- Is clinically significant in the investigator's judgment
- Requires a change in concomitant therapy (i.e. addition of, interruption of, discontinuation of, or any other change in a concomitant medication, therapy or treatment)

It is the investigator's responsibility to review all vital sign findings. Medical and scientific judgment should be exercised in deciding whether an isolated vital sign abnormality should be classified as an adverse event.

If a clinically significant vital sign abnormality is a sign of a disease or syndrome (e.g., high blood pressure), only the diagnosis (i.e., hypertension) should be recorded on the Adverse Event CRF.

Observations of the same clinically significant vital sign abnormality from visit to visit should not be repeatedly recorded on the Adverse Event CRF, unless the etiology changes. The initial severity of the event should be recorded, and the severity or seriousness should be updated any time the event worsens.

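### Version 2.1 names blood-pressure lowering and rare hypotension with dipyridamole but schedules no blood pressure measurement, so asymptomatic falls would be missed and no baseline or arm comparison will exist

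*Combined protocol and SAP*

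**What the plan says.** **Risk text.** Section 5.3 reports that dipyridamole given to dogs lowered vascular resistance in a dose-related way, "leading to decreases in systemic blood pressure and increases in coronary blood flow". It then adds: "In man the same qualitative hemodynamic effects have been observed". Section 5.5 lists among rare post-marketing reports "hepatitis, thrombocytopenia, alopecia, cholelithiasis, hypotension, palpitation, and tachycardia". The precaution that Section 5.5 states for the combination covers laboratory reports and bleeding.

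**Assessment text.** Section 12.4: "Vital signs will include measurements of body temperature, respiratory rate, heart rate and" SpO2. Section 9.11 begins its list "Vital signs (body temperature, respiratory rate, heart rate" and ends it with SpO2. The synopsis (3.1), footnote b of the Schedule of Activities (3.2) and the procedure notes in 9.2 name the same four measures. For remote assessment, subjects receive a thermometer and a pulse oximeter. On the physical examination, Section 9.11 says "Physical Examination (subject self-reported / examiner evaluated): At screening"; the contents listed in 12.3 do not include blood pressure.

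**A stray reference.** Section 12.5 does mention blood pressure, as its example of how to record a vital-sign finding: "If a clinically significant vital sign abnormality is a sign of a disease or syndrome (e.g., high blood pressure").

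**The concern.** The primary objective is the safety and tolerability of the combination, dipyridamole is the added component, and Section 5.5 says the combination has not been given to patients before. Section 15.5 makes vital signs one of the bases of the safety evaluation. Of the cardiovascular effects that Section 5.5 lists together, tachycardia can show up in a scheduled heart rate, but nothing scheduled can show hypotension.

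The blinding makes this matter a little more. Section 9.8 states that there is no dipyridamole placebo, so subjects can tell whether they are taking the tablets. Reports of symptoms may be coloured by that knowledge, and a blood pressure reading would be an objective check on them.

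At stake is how far the final report can be trusted on this effect. If it shows no hypotension, a reader cannot tell whether there was none or whether nobody looked.

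**Working it through.** The plan states no figure on this point and no power calculation (Sections 9.6 and 15.2). The check is mainly a comparison of text, with some arithmetic for scale.

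**1. Does any scheduled assessment measure blood pressure?**

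| Place in Version 2.1 | What is measured | Blood pressure |
|---|---|---|
| 3.1 synopsis (procedure notes, safety measures) | temperature, respiratory rate, heart rate, SpO2 | no |
| 3.2 footnote b | same four | no |
| 9.2 procedure notes | same four | no |
| 9.11 | same four | no |
| 12.4 | same four | no |
| 12.3 physical examination | body systems, at screening only, may be self-reported | not listed |

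The daily vital signs for hospitalised subjects use the same list. Version 01 has the same Section 12.4, so the list was left unchanged when the dipyridamole risk text was added in Version 2.1.

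**2. Which routes to detection remain?** Section 9.4 allows an unscheduled visit at any time. Section 9.11 allows extra examination at the investigator's discretion. Section 12.9 has subjects volunteer adverse events and be asked about them. Section 12.12 grades by symptoms, need for intervention and limits on daily activities, none of which needs a scheduled reading. A subject who feels faint can therefore be reported, examined and graded. A subject whose pressure falls without symptoms prompts none of these steps.

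**3. What would zero reported cases show?** Combination subjects: 8 per cohort; 4 × 8 = 32 in Part 1; 32 + about 32 in the expansion cohort = about 64, if all four cohorts and the expansion enrol. With zero cases among n subjects and every case seen, the one-sided 95% upper limit on the true rate is U = 1 − 0.05^(1/n):

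- n = 8: 1 − 0.05^(1/8) = 31.2%
- n = 32: 1 − 0.05^(1/32) = 8.9%
- n = 64: 1 − 0.05^(1/64) = 4.6%

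If only a fraction s of true cases is noticed, zero reports bound s × p rather than p, so the limit on p becomes U/s; halving s doubles the limit. The documents give no value for s. For asymptomatic falls s is close to zero, and zero reports then say almost nothing.

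**4. Could cases plausibly occur?** The chance of at least one case is 1 − (1 − p)^n. The documents give no rate, so p is assumed:

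| Assumed true rate p | n = 8 | n = 32 | n = 64 |
|---|---|---|---|
| 1% | 8% | 28% | 47% |
| 5% | 34% | 81% | 96% |
| 10% | 57% | 97% | 99.9% |

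**5. Who would have on-drug readings if blood pressure were added?** The PK subset is about 50% of each arm (Section 9.1): 4 combination, 2 brequinar and 2 placebo subjects per cohort. That reproduces the plan's approximately 8 per cohort and, over four cohorts, 32. Over four cohorts the PK draws would give Day 1 readings on 16 combination, 8 brequinar and 8 placebo subjects. Hospitalised subjects and any in-person contacts add to this.

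**The case against.** **The strongest case against** is that the risk is modest and the trial is not blind to it. The explicit blood-pressure statement concerns dogs; for man the text claims only qualitative similarity. Hypotension is listed as rare, and Section 5.5 describes reactions at therapeutic doses as generally slight and short-lived. Heart failure and uncontrolled cardiovascular disease are excluded. The high-blood-pressure example in 12.5 may be template text. The primary endpoint counts related Grade 3 and 4 toxicities and SAEs, and events that severe would normally present clinically. Section 12.5 also says that an abnormal vital sign is not automatically an adverse event. All of this stands, and it limits the size of the point.

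**Three stronger readings** might be inferred, and the documents do not support them.

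- *That hypotension cannot be detected or graded.* It can when it causes symptoms, by the routes in step 2.
- *That the gap distorts dose escalation by misclassifying dizzy subjects.* The rule in 12.9 counts subjects with any related adverse event, whatever its name. Related dizziness counts once whether it is called dizziness or hypotension.
- *That the 13.6% dizziness rate in Section 5.5 measures the problem.* That figure is for dizziness, not hypotension, in patients also taking warfarin, and it does not size this gap.

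**A practical objection also stands.** Dosing is on Days 1 to 5. Section 9.2 allows telephone contact on Days 2, 3 and 5 and a virtual visit on Day 4. For a subject neither hospitalised nor in the PK subset, the next default in-person visit is Day 8, after dosing has ended.

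**Conclusion.** The point holds in a limited form. Version 2.1 names blood-pressure lowering and hypotension as dipyridamole effects and schedules no blood pressure reading in any arm. What is lost is the systematic finding of asymptomatic falls, together with any baseline, change from baseline or comparison between arms. Symptomatic cases remain reportable and gradable. The consequence is that an absence of reported hypotension would be weak evidence: weaker than upper limits of 31.2% in a cohort of 8 and 4.6% in about 64, because those limits assume that every case is seen. They also assume full enrolment, including the expansion cohort.

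This is an inexpensive improvement to the safety data, not a flaw that undermines the trial. The absence of scheduled blood pressure is certain from the text. How often pressure would fall in these subjects is not known from the documents.

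**What to change.** Reconcile Sections 5.3, 5.5 and 12.5 with the vital-sign lists by adding seated blood pressure to 3.1, footnote b of 3.2, 9.11 and 12.4. Take it:

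- at screening and on Day 1 before dosing;
- at the Day 1 post-dose PK draws (1, 2, 4 and 8 hours), when staff are already with the subject;
- daily while hospitalised;
- at any in-person visit, including Days 2 to 5 when these are in person.

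Summarise values and change from baseline by arm, descriptively, and report how many subjects in each arm had an on-treatment reading. If the sponsor prefers not to measure blood pressure, the protocol should say why, and the report should not present an absence of hypotension as a finding.

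The cost is about a minute per in-person contact and one CRF field. Most on-treatment contacts for non-hospitalised subjects outside the PK subset may be remote, so on-drug readings will come mainly from hospitalised and PK subjects. The arm comparison will be small: 4 placebo subjects per cohort, about 2 of them in the PK subset, and no placebo arm in the expansion cohort.
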